#### **4.2.2 Incomplete dates for adverse events and concomitant medications**

For analyses of AEs and concomitant medication usage, a complete date must be established in order to correctly identify the AE or medication as occurring during treatment or not. For purposes of imputing missing components of partially-reported start and stop dates for AEs and for medication use, the algorithms listed below will be followed. Start and stop dates of AEs or concomitant medication will be displayed as reported in the subject data listings (ie, no imputed values will be displayed in data listings).

- Missing start day, but month and year present:  
If the start of LCM occurred in the same month and year as the occurrence of the AE/concomitant medication, the start day of the event/concomitant medication will be assigned to the day of first intake of LCM. Otherwise the start day will be set to the 1st day of the month.
- Missing start day and month, but year present:  
If the start of LCM occurred in the same year as the occurrence of the AE/concomitant medication, the start day and month will be assigned to the date of first intake of LCM. Otherwise the start day and month will be set to January 1st.
- Missing end day, but month and year present:  
The end day will be set to the last day of the month.
- Missing end day and month, but year present:  
The end day and month will be set to the maximum of the date of study termination or the date equivalent to 30 days after last intake of LCM.

However, if the study termination year and year for the date which is 30 days after last intake of LCM are greater than the event/concomitant medication year, the day and month are to be set to December 31st.

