#### **4.2.3 Definition of concomitant medication in case of missing dates**

With respect to definition of medication as concomitant, the following rule will be applied in case of completely missing stop and/or start date information:

Medications with a missing start date whose stop date is either unknown or after the date of the first dose of LCM will be considered as concomitant medication. Medications with missing start date whose stop date is prior to first intake of LCM will not be considered concomitant.

In subject data listings, dates will be displayed as reported.

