### 8.2 Adverse events

AEs will be tabulated by MedDRA SOC and MedDRA PT; select tables will also be presented by weight band and seizure classification subgroup using the levels defined in Sections 3.2.10 and 3.2.12, respectively. Additional tables will also be presented by time interval using the definition in Section 3.2.5. The number and percentage of study participants experiencing each event at least once will be summarized. All summaries will be sorted alphabetically by SOC and by frequency of events within PTs, starting with the most frequent event overall.

AEs will be classified as pre-treatment, treatment-emergent, or post-treatment. Pre-treatment AEs are defined as AEs which had an onset date prior to the first SP848 dose of LCM.

Treatment-emergent AEs (TEAEs) are defined as those events which started on or after the date of first SP848 dose of LCM, or whose intensity worsened on or after the date of first SP848 dose of LCM. AEs occurring within 30 days after last dose of LCM will be considered treatment emergent. Post-treatment AEs are defined as AEs which had an onset date after 30 days after the last dose of LCM.

For results disclosure on public registries (eg, ClinicalTrials.gov), treatment-emergent adverse events and treatment-emergent serious adverse events will be published.

All AEs reported during the study including pre-treatment and post-treatment AEs will be provided in a subject data listing.

An overview of the incidence of TEAEs will provide the overall summary of TEAEs and the numbers and percentages of study participants with at least 1 TEAE, with a serious TEAE, with a drug-related TEAE, with a severe TEAE, and with a drug-related serious TEAE. The number and percentage of subject discontinuations due to TEAEs, the number and percentage of all deaths (if applicable), and the number and percentage of study participants with AEs leading to death (if applicable) will also be summarized. This overall summary will be repeated by weight band and seizure classification subgroup using the levels defined in Sections 3.2.10 and 3.2.12 respectively. In addition, the overall summary will be presented for the Titration Period, Post-Titration Period and Treatment Period for the direct enrollers and the Treatment Period for the rollover study participants.

The following summaries of AEs will be provided by MedDRA primary SOC and PT:

- Incidence of TEAEs
- Incidence of TEAEs with onset during the Titration Period for direct enrollers

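### Section 4.2.2 moves a partial AE start date to the first SP848 dose without looking at the end date, so an event already over before dosing is counted as a TEAE

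*SAP*

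**What the plan says.** SAP Section 4.2.2 states its own purpose: "a complete date must be established in order to correctly identify the AE or medication as occurring during treatment or not".

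It then gives two rules for partial start dates that fall near the first dose:

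- Day missing, LCM started in the same month and year: "the start day of the event/concomitant medication will be assigned to the day of first intake of LCM".
- Day and month missing, LCM started in the same year: "the start day and month will be assigned to the date of first intake of LCM".

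The end-date rules stand apart from these. For a missing end day, "The end day will be set to the last day of the month". Nothing in the section requires the start to be no later than the end.

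Section 8.2 classifies by onset: "Treatment-emergent AEs (TEAEs) are defined as those events which started on or after the date of first SP848 dose of LCM", or worsened in intensity on or after that date. It also provides for the opposite class: "Pre-treatment AEs are defined as AEs which had an onset date prior to the first SP848 dose of LCM". Section 3.2.1.1 fixes first dose as the first dose in SP848, for rollover participants too. Section 2.3.1 lists TEAE incidence as a primary safety variable.

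**The concern.** Moving an uncertain onset to the first dose is a sensible cautious choice when the timing is unknown. It is not sensible when the end date settles the timing. An event known to have finished before the first SP848 dose cannot have started, or worsened, on or after it, so by Section 8.2's own logic it is pre-treatment. The rule makes it treatment-emergent and gives it an impossible date order.

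Such an event would carry an onset on Day 1. It would therefore appear in the interval up to 3 months and, for direct enrollers, in the Titration Period tables. Section 4.2.2 shows dates in the listings only as reported, so the imputed onset that produced the classification is not displayed.

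**Working it through.** The SAP gives no figure to reproduce here. The check is date logic: apply the Section 4.2.2 rules, then the Section 8.2 definition.

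**Does another section correct the result?**

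- Section 4.2.3 has the kind of check that is needed: "Medications with missing start date whose stop date is prior to first intake of LCM will not be considered concomitant". It covers medications with a completely missing start date, not AEs and not partial dates.
- Section 4.2.6 has a general earliest-date rule but lists AE start and stop dates as exceptions to it.
- Section 4.2.4 limits an imputed last LCM dose to the date of death. It is a plausibility check of the same type, but for a different date.

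None of these reaches a partial AE start date.

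**Worked cases.** The first SP848 dose is assumed to be 20 March 2015, for illustration only. Duration = end − start + 1 day.

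| Reported start | End date | Onset under 4.2.2 | Duration | Class under 8.2 |
|---|---|---|---|---|
| March 2015 | 10 March 2015 | 20 March 2015 | 10 − 20 + 1 = −9 days | TEAE |
| 2015 | 15 February 2015 | 20 March 2015 | −33 + 1 = −32 days | TEAE |
| 2015 | February 2015, imputed to 28 February | 20 March 2015 | −20 + 1 = −19 days | TEAE |
| March 2015 | 25 March 2015 | 20 March 2015 | 25 − 20 + 1 = 6 days | TEAE |

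The first three rows are wrong. The fourth is how the rule should behave.

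**All possible cases for that dose date.** Take every pair of true start and end dates that both fall before the dose, with the end date known.

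- Start known to the month: 19 days precede the dose (1 to 19 March), giving 19 × 20 / 2 = 190 pairs. All 190 become TEAEs with onset after their end.
- Start known to the year: 31 + 28 + 19 = 78 days precede the dose, giving 78 × 79 / 2 = 3081 pairs. All 3081 become TEAEs with onset after their end.

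With an end-date condition added, both counts fall to 0. The first case then has onset 1 March, the second and third have onset 1 January, and the fourth is unchanged. These counts show that the fault is systematic within the affected cell. They do not say how many trial records lie in that cell.

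**Boundary.** If start and end are both known only to the month of first dose, the end is imputed to the last day of that month. No impossible order arises, and the cautious imputation stands.

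**Year-only end date.** Section 4.2.2 says "The end day and month will be set to the maximum of the date of study termination or the date equivalent to 30 days" after the last LCM intake, with an override to 31 December only if both reference dates fall in a later year than the event. Suppose last dose and termination are both 15 December 2018 and the end is reported as 2018. Last dose + 30 days is 14 January 2019. The termination year, 2018, does not exceed 2018, so the override does not fire. The maximum then lies in a year the site did not report.

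**The case against.** The strongest reply is that the effect is small and on the cautious side. The study is single-arm and descriptive. Section 4.2.1 already takes the worst case for missing AE intensity and relationship, and this rule can add a TEAE but cannot hide one. Section 8.2 counts each participant once per event, so a false record changes overall TEAE incidence only if that participant has no other TEAE. Otherwise it alters a preferred-term row. All of this stands and limits the weight of the point. It does not justify counting an event that the data show was over before dosing.

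Four stronger readings are tempting, and the SAP does not support them.

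- *Medications ending before first dose are all misclassified as concomitant.* Sections 6.4.2 to 6.4.4 define concomitant use by intake at first dose, by at least one day shared with LCM, or by use during the Treatment Period. A medication stopped before first dose meets none of these, whatever start is imputed, so medications are largely protected.
- *Rollover participants are the most exposed.* Nothing in the SAP says that parent-study events resolved before the first SP848 dose are in the SP848 AE data. An event still ongoing at rollover does not trigger the fault.
- *The year-only end-date gap inflates TEAEs.* Section 8.2 does not use the end date, so it cannot.
- *The 100% misclassification rate measures the impact.* It follows from how the affected records are defined and says nothing about how common they are.

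**Conclusion.** The point holds for adverse events. Section 4.2.2, applied as written, turns any AE with a partial start in the first-dose month or year, and a reported or imputed end before the first SP848 dose, into a TEAE with onset after its own end. No other section of the SAP prevents this.

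The number of affected records cannot be derived from the document and is probably small. The direction is known: over-counting only. This rests on programming the rules literally. A programmer might add a date-order check unprompted, but the SAP does not ask for one. Because the rule feeds a primary safety variable and the correction costs almost nothing, it should be made. The year-only end-date gap is a separate wording matter with no bearing on TEAE counts.

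**What to change.** Add one condition to each of the two start-date rules in Section 4.2.2: if the reported or imputed end date is before first intake of LCM, set the start to the first day of the reported month when only the day is missing, or to 1 January of the reported year when day and month are missing. Leave the imputation unchanged where the end date is unknown or falls on or after first intake. Applying the same condition to medications keeps Section 4.2.2 consistent with Section 4.2.3 and with the overlap definitions in Section 6.4.

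As separate tidying, cap the year-only imputed end date at 31 December of the reported year.

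The cost is a clause in each start-date rule, a cap in the end-date rule, and the matching lines of code. No data collection changes. The TEAE count may fall slightly.

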#### **4.2.3 Definition of concomitant medication in case of missing dates**

With respect to definition of medication as concomitant, the following rule will be applied in case of completely missing stop and/or start date information:

Medications with a missing start date whose stop date is either unknown or after the date of the first dose of LCM will be considered as concomitant medication. Medications with missing start date whose stop date is prior to first intake of LCM will not be considered concomitant.

In subject data listings, dates will be displayed as reported.

#### **4.2.4 Incomplete dates for the last administration of LCM**

For purposes of imputing missing components of partially reported dates for the last administration of LCM, the algorithms listed below will be followed. Stop dates of LCM will be displayed as reported in the subject data listings (ie, no imputed values will be displayed in data listing).

- Missing last administration day, but month and year present:  
The last administration day will be set to the last day of the month or the date of the final contact, whichever is earlier in the month.
- Missing last administration day and month, but year present:  
The last administration day will be set to the last day of the year or the date of the final contact, whichever is earlier in the year.
- Completely missing date of last administration:

For calculating the duration of exposure, if the date of last administration is completely missing and no information could be obtained from data cleaning exercises, the date of last administration should be imputed as the date of last contact according to the Study Termination eCRF module. For all other purposes, no imputation will be done if the date of last administration is completely missing.

However, if a subject died during the study, and the imputed last administration date according to the rules above is after the date of death, the last administration date will be assigned to the date of death.

#### **4.2.5 Incomplete dates for seizure diary data**

Seizure frequency and seizure-free days will be calculated over non-missing diary days during each time interval; days for which seizure diary data were not obtained will not be considered in the calculation of seizure frequency or seizure-free days. As the evaluation of efficacy is not the primary objective of this study, and because this is an uncontrolled study in a variable setting, which allows individualized optimization of dosing of LCM and concomitant AEDs, no summaries assessing the impact of missing seizure diary days are planned.

#### **4.2.6 General imputation rule for incomplete dates**

Where necessary for the calculation of derived variables, partial dates will be completed using the earliest calendar date based on the partial date provided. This rule is valid for all partial dates with the exception of the following:

- Start and stop dates of AEs
- Start and stop dates of concomitant medication
- Start and stop dates of LCM
- Start and stop dates of seizure diary data

Completely missing dates will not be replaced and the corresponding derived variables will be set to missing.

#### **4.2.7 Missing data due to participation in solution for infusion formulation trials**

Study participants who participated in the iv trial EP0060 while also enrolled in SP848 will have missing data for seizure frequency and drug dosing during the period of participation in the iv trial. As the duration of the iv trial is short, approximately 1 to 5 days, no imputation for data missing due to participation in the iv trial will be performed.

Study participants were assigned the same dose in EP0060 as that assigned in SP848 for the two weeks prior to the start of the iv trial. As such, time during the iv trial will not be subtracted from the exposure calculation (ie, exposure will be from the start of LCM treatment in SP848 trial until the date of last dose of LCM in SP848). The duration of treatment during EP0060 is approximately 1 to 5 days.

For the calculation of variables related to seizure frequency, the dates during participation in EP0060 will be considered as not done for the purpose of efficacy analyses for SP848 (ie, the dates will not be considered as days evaluated for seizure frequency). Due to the short nature of

EP0060, only 1 to 5 days of seizure frequency data are expected to be missing due to participation in EP0060.

### **4.3 Interim analyses and data monitoring**

No formal interim analysis is planned. However, data may be reported prior to the completion of this study to support annual reports, regulatory submissions, and publications.

### **4.4 Multicenter studies**

No multicenter analyses are planned; therefore, this section is not applicable for this study.

### **4.5 Multiple comparisons/multiplicity**

No statistical testing is planned; therefore, this section is not applicable for this study.

### **4.6 Use of an efficacy subset of study participants**

The FAS, defined in Section 3.5.3, is the primary analysis set for efficacy analyses. No additional efficacy subsets are defined for this study.

### **4.7 Active-control studies intended to show equivalence**

This section is not applicable for this study.

### **4.8 Examination of subgroups**

Subgroups for this study are defined in the sub-sections of Section 3.2.

## **5 STUDY POPULATION CHARACTERISTICS**

### **5.1 Subject disposition**

The number of study participants screened (screened study participants include study participants who signed an ICF), in addition to the number and percentage of those study participants who were screen failures, broken down by primary reason for screening failure, will be presented. A summary of disposition of study participants will be provided for all screened study participants. The date of first subject in (date of earliest entry visit for the SP848 study), date of last subject out (date of final scheduled or unscheduled visit), number of study participants screened, number of study participants enrolled, and the number of study participants in each analysis set (SS, PK-PPS, and FAS), will be summarized overall and by investigator site. Study participants who transferred sites will be summarized according to their original site.

A summary of disposition of analysis sets will be provided for all screened study participants. The following will be summarized:

- The number of screened study participants
- The number and percentage of enrolled study participants
- The number and percentage of study participants in the SS
- The number and percentage of study participants in the PK-PPS
- The number and percentage of study participants in the FAS
- The number of study participants from each parent study

- The number of original direct enrollers (excluding Japanese and Chinese direct enrollers)
- The number of Japanese direct enrollers
- The number of Chinese direct enrollers

Additionally, a summary of disposition and discontinuation reasons will present the following for all study participants in the SS (overall and repeated by weight band and seizure classification subgroup using the levels defined in Sections 3.2.10 and 3.2.12, respectively), PK, PPS, and FAS:

The number and percentage of study participants starting the study

The number and percentage of study participants completing <12 months, 12, 24, 36, and ≥48 months of the study.

The number and percentage of study participants completing the study (defined as study participants who have ‘Completed subject’ selected as status at termination – see Study Termination eCRF module).

The overall number and percentage of study participants discontinuing and the number and percentage of study participants discontinuing by primary reason for discontinuation. If the subject discontinued the study and the Study Termination eCRF module is not available, the reason for discontinuation will be reported as “UNKNOWN”.

A summary of discontinuations due to AEs for all screened study participants will present the number and percentage of study participants who discontinued this study due to AEs broken down by type of AE.

The number and percentage of study participants enrolled under each protocol amendment (estimated by date of informed consent) will be presented for all global protocols, and separately, for Chinese direct enrollers from version 5.4 and for Japanese direct enrollers from version 5.3. This will also be presented in the subject data listings.

The number and percentages of subjects impacted by COVID-19 will be presented for each visit, overall and by impact category, for each relationship to COVID-19 as well as any relationship, overall and by country, for all subjects in the SS. This will also be presented in the subject data listings.

## 5.2 Protocol deviations

Important protocol deviations defined in the SPD, and additionally identified at the DRM, will be listed. In addition, the number and percentage of study participants with at least 1 important protocol deviation will be summarized overall and by category of important protocol deviation (as defined in Section 3.4) for the SS.

## 6 DEMOGRAPHICS AND OTHER BASELINE CHARACTERISTICS

### 6.1 Demographics and other Baseline characteristics

Demographic variables, unless otherwise specified, will be obtained from the demographics data collected at the time of entry into the previous pediatric LCM study for those study participants who enrolled from SP847 (or other LCM pediatric clinical studies in epilepsy). Demographic variables will be obtained from the Screening Visit for those study participants who directly enrolled into SP848.

Demographic variables will be presented by weight band (using the levels defined in Section 3.2.10), by seizure classification subgroup (using the levels defined in Section 3.2.12) and overall for the SS. The variables to be considered are:

- Age at entry into SP848 (as defined in Section 3.2.9) – continuous and categorized as (28 days - <24 months, 24 months - <12 years, 12 years - <18 years) and categorized as ( $\leq 18$  years and 19 - < 65 years)
- Age at entry into previous pediatric study for study participants from SP847 or other studies and age at entry into SP848 for directly enrolled study participants (years) (as defined in Section 3.2.9)
- Gender
- Weight (kg) at entry into SP848
- Weight band (as defined in Section 3.2.10)
- Height (cm)
- BMI ( $\text{kg}/\text{m}^2$ ) (as defined in Section 3.2.11)
- Racial group (American Indian/Alaskan Native, Asian, Black, Native Hawaiian or Other Pacific Islander, White, and Other/Mixed)
- Ethnicity (Hispanic or Latino, and not Hispanic or Latino)
- Vagus nerve stimulation (VNS) use (Active VNS, No VNS, and VNS not active)

A listing of reproductive potential and birth control measures will be provided. No summaries of these results are planned.

### 6.2 Medical history and concomitant diseases

#### 6.2.1 Medical history

The number and percentage of study participants with a medical history condition (except epilepsy), including both resolved and ongoing conditions, will be summarized overall and by MedDRA® primary system organ class (SOC) and preferred term (PT) for the SS.

